STATISTIC

The results obtained from clinical, instrumental and subjective evaluations will be compared between experimental timepoints and later between treatments.

The hypothesis tests used in the study will have a 95% significance level and the statistical power of these tests will be above 80%.

➤ Study Variables

Primary Variables

- To evaluate the treatment superiority with the Exímia Probiac® product associated with the Epiduo® product use versus placebo use and Epiduo® on the success rate of the participants percentage with a reduction in the total number of inflammatory and non-inflammatory lesions in the facial region.
- To evaluate the treatment superiority with the Exímia Probiac® product associated with the Epiduo® product use versus placebo use and Epiduo® on the success rate of the participants percentage with regression of the IGA scale score to grade 1 or zero.

Secondary Variables

- To compare the treatment with the Exímia Probiac® product associated with the Epiduo® product use versus placebo use and Epiduo® on the response rate of the individuals percentage who had regression of the IGA scale score.
- To compare the treatment with the Exímia Probiac® product associated with the Epiduo® product use versus placebo use and Epiduo® on the perceived efficacy of the volunteer, evaluated through subjective questionnaires.
- To compare the treatment with the Exímia Probiac® product associated with the Epiduo® product use versus placebo use and Epiduo® on the evaluation of dilated pores and inflammatory lesions through photographic records and analysis of the Visia® equipment software.

➤ Statistical Methodology

• Primary Variables data analysis

First, we will perform descriptive analyses of the study variables through frequency tables and descriptive statistics (means, standard deviation, minimum, maximum and quartiles).

The percentage of participants with a reduction in the total number of inflammatory and non-inflammatory lesions, the percentage of participants with regression of the IGA scale score to cured (zero score) or almost cured (score one) will be evaluated through the *z test* for comparison of two proportions. The tested hypotheses will be:

$$H_0: \text{Perci}(P + E) \leq \text{Perci}(E)$$

$$H_a: \text{Perci}(P + E) > \text{Perci}(E)$$

Where Percc is the percentage of participants for each study variable.

• Secondary Variables data analysis

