In order to evaluate the individuals percentage who presented regression of the IGA scale score, primarily a data descriptive analysis will be performed and subsequently the evaluation through the z test for two proportions.

Ho: $\text{Perci}(P + E) \leq \text{Perci}(E)$

Ha: $\text{Perci}(P + E) > \text{Perci}(E)$

Where Percc is the percentage of participants for each study variable.

The comparison between treatments of perceived efficacy evaluated through a subjective questionnaire and counting the number of inflammatory lesions and dilated pores will be carried out using the Mann Whitney test, which is the most suitable for evaluating ordinal data from independent samples. The tested hypotheses will be:

Ho: $\text{Medj}(P + E) = \text{Medj}(E)$

Ha: $\text{Medj}(P + E) \neq \text{Medj}(E)$

Where Medj is the median of the results of each study variable.

The results will be considered statistically significant at a significance level of 5% (P value ≤ 0.05). The significance level will be controlled by rejecting the null hypotheses if the p Value is less than or equal to 5%.

For the analysis of pores and inflammatory lesions through the Visia® equipment, the equipment's raw data will be exported regarding the parameters quantification of each participant in their respective experimental time. The Anderson-Darling normality test will be applied to identify the data normality. According to the samples distribution result, it will be checked whether there is a difference between the experimental timepoints:

- Parametric tests - *t-student* for paired data to compare experimental timepoints if the normality hypothesis is not rejected;
- Nonparametric tests - *Wilcoxon* for paired data to compare experimental timepoints and *Mann-Whitney*, in case normality is rejected.

Subsequently, the results will be compared between experimental timepoints and later between treatments.

The results will be considered statistically significant at a 5% significance level (P value ≤ 0.05). The significance level will be controlled by rejecting the null hypotheses if the p Value is less than or equal to 5%.

The data collected in the studies will be evaluated according to the statistical methodology described and primary and secondary study variables, after the participants return from D60, D90 visits and the final visit D180.

➤ Sample Design

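### The 5% rule for the secondary variables limits each test only; nothing ties those tests to primary success or labels them supportive

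*SAP*

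**What the plan says.** The Secondary Variables part of Study Variables lists three items: the rate of IGA regression; the volunteer's view, described as "on the perceived efficacy of the volunteer, evaluated through subjective questionnaires"; and pores and inflammatory lesions measured with the Visia equipment. The third covers two measures, so there are at least four comparisons between treatments.

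The Secondary Variables data analysis section assigns the tests:

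- IGA regression: descriptive analysis and "subsequently the evaluation through the z test for two proportions", with a one-sided alternative in favour of the combination.
- The remaining variables: "perceived efficacy evaluated through a subjective questionnaire and counting the number of inflammatory lesions and dilated pores will be carried out using the Mann Whitney", with a two-sided alternative.

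The same section gives the decision rule twice, in near-identical words. The first time it reads "The results will be considered statistically significant at a significance level of 5% (P value ≤ 0.05"), followed by "The significance level will be controlled by rejecting the null hypotheses if the p Value is less than or equal to 5" per cent.

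The only other general statement on error is at the start of the SAP: "The hypothesis tests used in the study will have a 95% significance level and the statistical power of these tests will be above 80" per cent. The 95% there evidently means 5%, the level used everywhere else.

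The SAP has no ordering of the secondary variables, no condition that a primary variable must succeed first, no division or adjustment of the significance level, and no statement that secondary results are descriptive, supportive or exploratory.

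**The concern.** A threshold of 5% applied to each test fixes the false-positive rate of that one test. When several tests are each allowed to yield a significant result, the chance that at least one does so by luck is larger than 5%. The SAP says the level is controlled, but the mechanism it names works one test at a time.

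What is at stake is how a mixed outcome may be reported. If neither primary variable succeeds, the SAP as written still allows any secondary result with P ≤ 0.05 to be called statistically significant, with the same standing as a primary result. The secondary hypotheses are set out as formally as the primary ones, and IGA regression even carries the same one-sided superiority form. Nothing in the text tells the reader of the final report to give these results less weight.

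This is separate from how the two primary variables share the significance level and from the choice among the three analysis visits. If both were settled, the secondary variables would still be tested without gate or order.

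**Working it through.** **Inputs from the SAP**

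- Per-test level: 5%, unadjusted (Secondary Variables data analysis).
- Secondary between-treatment tests: four. One is one-sided (IGA regression); three are two-sided (perceived efficacy, inflammatory lesions, pores).
- Primary tests: two, both one-sided z tests (Primary Variables data analysis), taken at 5% each.

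**Assumptions not in the SAP**

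- One visit only.
- No true effect on any variable.
- Normal test statistics with a common correlation of 0, 0.3, 0.5 or 0.7.
- One test for perceived efficacy.

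**The stated figure.** For a single test, the false-positive rate is 5% by construction. The stated level therefore holds per test.

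**The set of four, independent tests**

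- At least one significant in either direction: 1 − 0.95⁴ = 1 − 0.8145 = 18.5%.
- At least one significant in favour of the combination. The one-sided test contributes 5%, and each two-sided test contributes 2.5% in that direction: 1 − 0.95 × 0.975³ = 1 − 0.8805 = 11.9%.
- Neither primary significant: 0.95² = 0.9025.
- Favourable significant secondary and no significant primary: 0.9025 × 0.1195 = 10.8%.

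**Correlated tests.** These were simulated with critical values 1.645 (one-sided) and 1.96 (two-sided). The two primaries were included for the last column.

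| Assumed correlation | Any significant secondary | At least one favouring the combination | Favourable secondary, neither primary significant |
|---|---|---|---|
| 0 | 18.5% | 11.9% | 10.8% |
| 0.3 | 17.5% | 10.8% | 8.2% |
| 0.5 | 16.0% | 9.7% | 6.1% |
| 0.7 | 13.6% | 8.2% | 3.9% |

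The first column answers how often the secondary set yields any false significance. The last column measures the situation described in the concern, and it is clearly smaller. It falls with correlation because a chance imbalance that makes a secondary significant then tends to make a primary significant as well.

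**Would a gate on the primaries be enough?** If success on either of two unadjusted primaries opened the gate, it would open under the null in 1 − 0.95² = 9.75% of trials when they are independent (8.1% at correlation 0.7). That exceeds 5% before any secondary is tested. If both primaries must be significant at 5%, followed by a fixed order at 5% each with a stop at the first non-significant result, the chance of any false claim stays at or below 5%.

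**Adjustment instead of order.** Bonferroni over four tests uses 0.05 / 4 = 0.0125 each. The error over the set is 1 − 0.9875⁴ = 4.9% if the tests are independent, and at most 5% in any case.

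**The case against.** The strongest reply is that the sentence is a per-test decision rule and nothing more. The SAP uses the term significance level for single tests throughout and never mentions family-wise or overall error. A reader might infer that it promises control over the whole secondary set and then breaks that promise. The text does not support this: read literally, the sentence is clumsy but true. What stands is that the word controlled invites the wider reading, and that no other provision covers the set.

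A second reply is that secondary variables tested at a nominal 5% are common and usually read as supportive. The SAP also distinguishes the two tiers: the primaries are there to evaluate superiority, the secondaries to compare. That is fair, and unadjusted secondary tests would be acceptable if labelled supportive. But the label is missing, and the decision rule is the opposite of one.

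Three further inferences go beyond the documents:

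- *That a failed trial would yield marketing or product claims.* The SAP speaks only of results being considered significant and says nothing of claims.
- *That the questionnaire is an especially weak basis for a significant result.* The Randomization section describes a double-blind comparison with placebo, which protects subjective answers as well.
- *That the number of tests is much larger because each questionnaire item is tested.* The SAP gives no item count. The variable list speaks of questionnaires in the plural, while the methods section describes one: "The comparison between treatments of perceived efficacy evaluated through a subjective questionnaire and counting the number of inflammatory lesions and dilated pores". Figures for many items would rest on a guess.

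High correlation is also plausible for some pairs. IGA regression and the primary IGA success rate come from the same scale, which pulls the relevant risk towards the lower end of the range.

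**Conclusion.** The point holds in a limited form. The SAP controls error per test, applies that rule to at least four secondary comparisons, and neither links them to the primary variables nor labels them supportive. At one visit with no true effect, the chance of at least one false significant secondary is about 16 to 19% at correlation 0 to 0.5, or 10 to 12% in favour of the combination. The chance of a favourable significant secondary when neither primary is significant is about 6 to 11%, and about 4% at correlation 0.7, which is below the nominal level.

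The sizes depend on the assumed correlations and on counting one visit and one questionnaire test. That the error over the set exceeds 5% does not depend on the correlations examined: it is still 13.6% at 0.7. The matter is worth correcting because it affects what the trial may conclude. It is not a failure to keep a stated family-wise guarantee, since none is stated.

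**What to change.** In the Secondary Variables data analysis section:

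1. Keep P ≤ 5% as the threshold for a single test, and state it in the primary section as well. The primary section has no rejection rule of its own, so the sentence should not simply be deleted.
2. Remove the suggestion that this threshold controls error over the set of secondary variables.
3. State that secondary p-values are nominal and supportive and do not support a confirmatory claim of significance.

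If the sponsor wants confirmatory secondary claims, replace item 3 by a testing sequence. Secondary variables are tested only after both primary variables succeed at one visit named in advance. They are then tested in an order fixed in advance, each at 5%, stopping at the first non-significant result. The order is the sponsor's choice but must be set before unblinding. This route requires the SAP to define the primary success criterion and the deciding visit, which it does not do now. A gate opened by either unadjusted primary would not suffice.

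The cost is SAP wording, with no change to patients, data or sample size. The downside is that a secondary result after a failed primary or a failed step cannot be called significant. Under the simpler option, no secondary result can be presented as confirmatory.

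### For the Visia parameters, an Anderson-Darling gate on an unspecified quantity picks the timepoint test, so the test can change between visits and arms, and the between-arm test is left unclear

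*SAP*

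**What the plan says.** All of this is in the SAP, Statistical Methodology, under the analysis of secondary variables, unless another place is given.

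- Data: "the equipment's raw data will be exported regarding the parameters quantification of each participant in their respective experimental time". No change score or paired difference is defined.
- Gate: "The Anderson-Darling normality test will be applied to identify the data normality". The level of this test is not given. Nor is it said whether it is run once or per parameter, visit and arm.
- Use of the gate: "According to the samples distribution result, it will be checked whether there is a difference between the experimental timepoints".
- Branch 1: "Parametric tests - *t-student* for paired data to compare experimental timepoints if the normality hypothesis is not rejected". No between-arm test is named here.
- Branch 2: Wilcoxon "for paired data to compare experimental timepoints and *Mann-Whitney*, in case normality is rejected".
- Timing: the data are evaluated "after the participants return from D60, D90 visits and the final visit D180".

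An earlier paragraph of the same section assigns the between-treatment comparison of inflammatory-lesion and dilated-pore counts to Mann-Whitney, with no normality condition. Under Study Variables, dilated pores occur only in the Visia item, and that item is a comparison of treatments.

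**The concern.** A paired t test is a one-sample t test on within-person differences. The shape of the values at a single visit is not its assumption. Values can be skewed while their differences are normal, and the reverse. A gate on the exported values can therefore reject the t test for a reason that does not bear on it, or pass it when the differences are badly skewed.

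The two branches also test different things: a mean change, or a signed-rank shift. If the gate is applied separately by visit and arm, one Visia parameter may be reported as a mean change at one visit and a rank shift at the next, or differently in the two arms. The time course then no longer reads on one scale, and the SAP has no rule for discordant gate results.

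The ambiguity reaches the stated Visia objective, which is between treatments. If normality is not rejected, the Visia paragraph offers no between-arm test, while the earlier paragraph gives Mann-Whitney regardless.

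**Working it through.** The SAP states no figure on this point, so there is none to reproduce. The check is by simulation.

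**Inputs from the SAP.** 200 participants per group (Sample Design); visits D60, D90 and D180; significance level 5%.

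**Assumptions.** A baseline visit, making four timepoints; a 5% level for the gate as well; all distributions and correlations, because the SAP gives no Visia mean, SD, skewness or correlation. Mild skew is a gamma distribution of shape 80 to 10 (skewness 2/√shape: 2/√80 = 0.22, 2/√10 = 0.63). Strong skew is shape 4 (2/√4 = 1.0).

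**1. Does the quantity checked matter?** (n = 200, 3,000 runs)

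| Scenario | Normality rejected, raw values | Normality rejected, differences |
|---|---|---|
| Skewed raw values, normal differences | 98.5% | 4.9% |
| Near-normal raw values, skewed differences | 5–6% | 100% |

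A gate that rejects when either timepoint rejects disagrees with a gate on the differences in 94.6% and 91.3% of comparisons respectively. The two gates are not interchangeable.

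**2. How often would the branch change over four visits?** Let r be the chance that the gate rejects at one visit. With independent visits,

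P(mixed) = 1 − r⁴ − (1 − r)⁴

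- Shape 80, r = 0.147: 1 − 0.0005 − 0.5294 = 0.47
- Shape 20, r = 0.469: 1 − 0.0484 − 0.0795 = 0.87
- Shape 10, r = 0.784: 1 − 0.3778 − 0.0022 = 0.62
- Shape 4, r = 0.998: 1 − 0.9920 − 0.0000 = 0.008
- Normal, r = 0.05: 1 − 0.0000 − 0.8145 = 0.19

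The visits are repeated measures on the same people, so independence overstates the switching. With correlated gamma values (Gaussian copula, 1,000 runs):

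| Shape | Correlation 0.8 | Correlation 0.9 |
|---|---|---|
| 80 | 38% | 34% |
| 20 | 67% | 53% |
| 10 | 43% | 35% |

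A repeat at correlation 0.8 gave 35 to 67% over these shapes and about 1% for strong skew. The 19% for normal data is the independent-visit value, so it is an upper guide.

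**3. A second correlated model.** Here a shared participant effect is combined with normal visit noise, over three baseline-to-visit comparisons, and the gate rejects if either timepoint rejects. Under mild skew (participant effect gamma shape 30, noise SD 2, so correlation 30/34 = 0.88), the test differs across the three visits in 23.0% of runs and between the two arms at one visit in 44.8%. With all data normal (correlation 4/5 = 0.8), it differs across visits in 12.2%. With strong skew, it differs in 0.8%.

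**4. Does the branch matter for the result?**

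- Normal differences, standardised change 0.2, n = 200: power 80.6% for paired t and 78.6% for Wilcoxon (80.3% and 78.9% in a repeat). With no change, both reject 5.3%.
- Skewed differences with mean zero (centred exponential), n = 200: paired t rejects 5.7% and Wilcoxon 64.3% (65% in a repeat). The mean has not moved but the distribution is not symmetric about zero, so the two tests answer different questions and the branch can decide the conclusion.

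**The case against.** The strongest reply has four parts.

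- **The SAP does not say that raw values are tested.** Exporting raw data is a data-handling step, and the text does not exclude testing differences. This stands. A reader might infer that the plan demonstrably checks the wrong quantity; the wording supports only that the quantity is unstated and most naturally read as the exported values. The per-visit, per-arm level of the gate is likewise unstated, so the switching figures are conditional on it.
- **Diversion to Wilcoxon is often harmless.** This stands for symmetric differences: the near-certain rejection under strong skew sends the analysis to a valid test at a cost of about 2 power points. It does not stand for skewed differences.
- **Diversion and switching do not peak together.** This also stands. Under strong skew the gate acts almost as a fixed Wilcoxon rule, with about 1% mixed branches; switching is a feature of mild skew.
- **The treatment comparison may be untouched**, because an ungated Mann-Whitney is named for lesion and pore counts. This stands in part. The Visia paragraph names Mann-Whitney again, but only after normality is rejected, and then also promises a comparison between treatments. The two paragraphs do not settle which rule governs.

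A reader might also infer that the plan lets the analyst choose the test freely after seeing the data. It does not: both tests and the trigger are written in advance. The latitude lies in the unstated variable and level of the gate.

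**Conclusion.** The concern holds in limited form. The SAP lets a normality test on an unspecified quantity, most naturally the exported values, select between two tests that do not target the same quantity, and gives no rule for discordant results across visits and arms. If the gate is run by visit and arm, mixed branches over four visits would occur in about 35 to 67% of runs under mild skew with visit correlation 0.8, about 1% under strong skew, and about 19% or less with normal data. Every one of these figures rests on assumed distributions, and the lower three-visit results (23.0% under mild skew, 12.2% with normal data) show how far they depend on the model. The consequence is small when differences are symmetric and potentially decisive when they are skewed.

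The paired t test itself is not at risk of gross error at 200 per arm (5.7% in the skewed case). The problem is an unstable target for the timepoint comparisons and an unclear between-arm test. Severity is modest: the endpoint is secondary, the primary analyses are unaffected, and the correction is cheap.

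**What to change.** In the Visia paragraph of the SAP:

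1. Delete the Anderson-Darling gate.
2. Define the analysed quantity for each Visia parameter as within-person change from baseline.
3. Name one test in advance for timepoint comparisons, the same at all visits and in both arms. For example, use mean change with 95% CI and a paired t test, with Wilcoxon signed-rank as a stated sensitivity analysis. Fixing Wilcoxon as the main test would serve equally to remove the switching.
4. Name one between-arm test on the same change, and make the two paragraphs agree. For example, keep the ungated Mann-Whitney and apply it to the change.

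The cost is SAP wording only; no new data are needed. The downside is some loss of efficiency for the t test if the differences are heavy-tailed, which the sensitivity analysis would show.

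### The between-treatment analysis of the secondary Visia outcomes names no baseline covariate and leaves the compared quantity open; an ANCOVA would gain precision at little cost

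*SAP*

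**What the plan says.** Under Study Variables, the third secondary objective compares the two treatments "on the evaluation of dilated pores and inflammatory lesions through photographic records and analysis of the Visia® equipment software". It is therefore a between-arm objective.

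Statistical Methodology (Secondary Variables data analysis) treats it in two places:

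- The paragraph on the subjective questionnaire says that the comparison between treatments, including "counting the number of inflammatory lesions and dilated pores will be carried out using the Mann Whitney test", has a two-sided hypothesis on medians. The quantity is described only by "Where Medj is the median of the results of each study variable".
- The Visia paragraph exports raw parameter values per participant and timepoint and applies an Anderson-Darling test, after which "it will be checked whether there is a difference between the experimental timepoints". One branch is a t test "for paired data to compare experimental timepoints if the normality hypothesis is not rejected". The other lists the paired Wilcoxon test and Mann-Whitney, "in case normality is rejected". The paragraph closes with "Subsequently, the results will be compared between experimental timepoints and later between treatments".

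The data are to be evaluated after D60, D90 and D180, and no visit is marked as the key one for Visia. No baseline covariate is named anywhere in the SAP. Sample Design fixes 200 participants per group.

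**The concern.** Pore and lesion measurements on the same face usually vary widely between people, and a person's starting value then predicts the later one. A between-arm test on the visit value alone leaves that variation in the error term. Mann-Whitney on the change removes some of it, but adds noise when the correlation with baseline is low. ANCOVA on the baseline value does at least as well as either under normal theory.

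Two things are at stake, both for a secondary outcome only. The first is precision: a real difference in pores or lesions may be missed that the same data could have shown. The second is that visit value, change and percentage change can give different p-values from the same data, and the SAP does not settle which one the word results refers to.

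**Working it through.** **No plan figure to reproduce.** The SAP gives no effect, SD, correlation or power calculation for Visia. Its 200 per group was derived for responder proportions and is taken here as given.

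**Inputs.** From the SAP: n = 200 per arm, 5% level, two-sided alternative. Assumed: normal data, equal variances, all 200 analysed, true difference d = 0.25 SD of the visit value, baseline-to-follow-up correlation ρ = 0.3, 0.5, 0.7 or 0.8.

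**Formulas.** Power = Φ(ncp − 1.960), with √(200/2) = 10:

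- Mann-Whitney on visit value: ncp = 10d√(3/π) = 2.5 × 0.977 = 2.443, so power = Φ(0.483) = 68.5%.
- Mann-Whitney on change: ncp = 2.443/√(2(1−ρ)).
- ANCOVA: ncp = 2.5/√(1−ρ²). At ρ = 0.5 this is 2.5/0.866 = 2.887, so power = Φ(0.927) = 82.3%.

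| ρ | MW, visit value | MW, change | ANCOVA | Gain over visit value | Gain over change |
|---|---|---|---|---|---|
| 0.3 | 68.5% | 54.2% | 74.6% | 6.1 | 20.4 |
| 0.5 | 68.5% | 68.5% | 82.3% | 13.8 | 13.8 |
| 0.7 | 68.5% | 88.4% | 93.8% | 25.3 | 5.4 |
| 0.8 | 68.5% | 97.1% | 98.6% | 30.1 | 1.5 |

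**Smallest difference detectable with 80% power.** Let k = (1.960 + 0.842)√(2/200) = 0.280.

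- Mann-Whitney on visit value: k/√(3/π) = 0.287 SD.
- Mann-Whitney on change: 0.287√(2(1−ρ)) = 0.339/0.287/0.222/0.181 SD.
- ANCOVA: k√(1−ρ²) = 0.267/0.243/0.200/0.168 SD.

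**Equivalent sample size.** ANCOVA matches Mann-Whitney on the visit value at 200(1−ρ²)(3/π) = 174/143/97/69 per arm.

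**Other effect sizes.** Over d = 0.15 to 0.35 SD, the gain of ANCOVA over Mann-Whitney on the visit value is 3–6 points at ρ = 0.3, 5–14 at 0.5, 7–30 at 0.7 and 7–42 at 0.8.

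**Skewed counts.** Lognormal-Poisson simulation, 3,000 trials per setting. Assumed: baseline mean 30, follow-up mean 18, log-SD 0.5, 14% fewer with P+E.

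| Log-scale correlation | MW, visit value | MW, change | MW, percentage change | ANCOVA, log(count+1) |
|---|---|---|---|---|
| 0.30 | 73.9% | 37.0% | 62.2% | 78.1% |
| 0.49 | 74.3% | 44.5% | 74.4% | 85.7% |
| 0.68 | 73.9% | 59.0% | 91.4% | 94.7% |
| 0.77 | 72.9% | 68.5% | 97.6% | 98.1% |

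With no true difference, ANCOVA rejects in 4.7–5.1% of trials and the Mann-Whitney versions in 4.1–5.7%. The type I error is therefore held near 5% by all of them.

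**The case against.** The other side has four good points.

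- **The test is named.** A reader might infer a contradiction, because Mann-Whitney is unconditional in one paragraph and tied to non-normality in the next, whose normal branch holds only a paired test. The text does not bear that out. The unconditional sentence is expressly about comparing treatments and most naturally governs the arms, while the Anderson-Darling list is introduced as a check between timepoints. For the assumed skewed counts the distinction hardly matters: Anderson-Darling rejected normality in 100% of simulated trials for the visit value, 96–100% for change and 99–100% for percentage change. Both readings then lead to Mann-Whitney.
- **No power shortfall is shown.** The opening section promises that "the statistical power of these tests will be above 80" per cent, and a reader might set 68% against it. But 0.25 SD is an assumption, and at 0.287 SD Mann-Whitney on the visit value has 80% power. Without a Visia effect or SD in the SAP, the promise can be neither confirmed nor refuted for these outcomes.
- **The visit value is the natural reading.** The export is of raw values per timepoint and no derived Visia variable appears. Percentage change is mentioned only in Sample Design, for the primary hypothesis. The protocol, not shown, may define the measure.
- **An unadjusted rank test is valid in a randomised trial.** Choosing it is not an error.

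All four stand, and they confine the point to precision and one missing definition. They do not remove it: if the visit value is indeed meant, the baseline is ignored altogether, which is where ANCOVA gains most at moderate or high correlation.

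**Conclusion.** The point holds as a cheap improvement for a secondary outcome. The planned between-arm comparison of the Visia parameters is valid but makes no use of a baseline covariate, and the quantity compared should be written down. At an assumed 0.25 SD, ANCOVA gains about 6 to 30 power points over Mann-Whitney on the visit value and about 2 to 20 over Mann-Whitney on change. The assumed skewed counts give the same direction, though against percentage change the advantage falls to half a point at the highest correlation.

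These sizes rest on assumed effects, distributions and correlations, and on a full 200 per arm. The benefit also depends on a pre-treatment Visia measurement. The paired timepoint tests suggest one exists, but the SAP names only D60, D90 and D180. The primary analyses and the type I error are not in question.

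**What to change.** Before unblinding, amend Secondary Variables data analysis as follows:

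1. Confirm that a pre-treatment Visia measurement is taken, and state it.
2. For each Visia parameter, make the between-arm analysis an ANCOVA of the follow-up value on arm and baseline value, on a scale fixed in the SAP (for example log(count+1) for counts).
3. Name one key visit among D60, D90 and D180, and call the others supportive.
4. Keep Mann-Whitney as a sensitivity analysis and state whether it uses the visit value, the change or the percentage change.
5. Limit the Anderson-Darling switch to the within-arm timepoint tests.

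If ANCOVA is not wanted, the minimum is one sentence naming one two-sample test and the quantity it is applied to.

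The cost is SAP wording and a standard regression on data already due for export. The downside is a linear-model assumption, against which the retained rank test is a check.
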